### **7.6.5 Adverse Events**

Adverse events will be summarized by treatment group.

The following analyses will be conducted using the 30 days safety window only:

- Overall summary of any AEs by worst CTC grade (1, 2, 3, 4, 5, not reported, total) presented by SOC/PT. This output will also be presented for CPS  $\geq 5$  treated subjects.
- Overall summary of any AEs presented by worst CTC grade (any grade, grade 3-4, grade 5) by SOC/PT. This table will be restricted to events with an incidence greater or equal to 5% in any treatment group. This output will also be presented for CPS  $\geq 5$  treated subjects.
- Overall summary of any non-serious AEs presented by SOC/PT. This table will be restricted to events with an incidence greater or equal to 5% in any treatment group.
- Overall summary of any AEs that required immune modulating medication by worst CTC grade (any grade, grade 3-4, grade 5) presented by SOC/PT.
- Overall summary of drug-related AEs by worst CTC grade (1, 2, 3, 4, 5, not reported, total) presented by SOC/PT. This output will also be presented for CPS  $\geq 5$  treated subjects.
- The following analyses will be conducted using the 30 days safety window and repeated using the 100 days safety window:
- Overall summary of drug-related AEs by worst CTC grade (any grade, grade 3-4, grade 5) presented by SOC/PT. This output will also be presented for CPS  $\geq 5$  treated subjects.

A by-subject AE listing will be provided. A by-subject listing of any AE requiring immune modulating medications will also be provided.

#### **7.6.6 Select Adverse Events**

Unless otherwise specified, analyses will be performed by select AE category. Analyses will also be repeated by subcategory of endocrine events.

##### **7.6.6.1 Incidence of Select AE**

Select AEs will be summarized by treatment group for each category/subcategory.

The following analyses will be conducted using the 30-day safety window only:

- Overall summaries of any select AEs by worst CTC grade (any grade, grade 3-4, grade 5) presented by Category or Subcategory/PT. This output will also be presented for CPS  $\geq 5$  treated subjects.
- Overall summaries of any drug-related select AEs by worst CTC grade (any grade, grade 3-4, grade 5) presented by Category or Subcategory/PT. This output will also be presented for CPS  $\geq 5$  treated subjects.
- Overall summaries of any serious select AEs by worst CTC grade (any grade, grade 3-4, grade 5) presented by Category or Subcategory /PT.
- Overall summaries of drug-related serious select AEs by worst CTC grade (any grade, grade 3-4, grade 5) presented by Category or Subcategory /PT.
- Overall summaries of any select AEs leading to discontinuation by worst CTC grade (any grade, grade 3-4, grade 5) presented by Category or Subcategory /PT.
- Overall summaries of drug-related select AEs leading to discontinuation by worst CTC grade (any grade, grade 3-4, grade 5) presented by Category or Subcategory /PT.
- Summary of frequency of unique select AEs by Category.

A by-subject select AE listing will be provided.

#### **7.6.6.2 Time-to Onset of Select AE**

Time-to onset of drug-related select AEs (any grade, grade 3-5) will be summarized for each category/subcategory by treatment group.

Time-to onset analyses are restricted to treated subjects who experienced at least one drug-related select AE in the category/subcategory. The analyses will be conducted using the 30-day safety window.

Additional details regarding the time-to onset definition are described in time-to onset definition subsection of [APPENDIX 1](#).

#### **7.6.6.3 Time-to Resolution of Select AE**

Time-to resolution of the following specific events will be summarized separately for each category/subcategory.

- Time-to resolution of drug-related select AE (any grade, grade 3-5) by treatment group
- Time-to resolution of drug-related select AE (any grade, grade 3-5) where immune modulating medication was initiated, by treatment group

Time-to resolution analyses are restricted to treated subjects who experienced the specific events. Time-to resolution where immune modulating medication was initiated analyses are restricted to treated subjects who experienced the specific events and who received immune modulating medication during the longest select AE.

The analyses will be conducted using the 30-day safety window.

The following summary statistics will be reported: percentage of subjects with resolution of the longest select AE, median time-to resolution along with 95% CI (derived from Kaplan-Meier estimation) and ranges.

See time-to resolution definition subsection of [APPENDIX 1](#) for additional details.

#### **7.6.7 Immune-Mediated Adverse Events**

IMAEs will be summarized by treatment group for each immune-mediated category / PT using the 100-day safety window:

- Overall summary of non-endocrine IMAEs by worst CTC grade (any grade, grade 3-4, grade 5) where immune modulating medication was initiated presented by Category / PT. This output will also be presented for CPS  $\geq 5$  treated subjects.
- Overall summary of endocrine IMAEs by worst CTC grade (any grade, grade 3-4, grade 5) presented by Category / PT. This output will also be presented for CPS  $\geq 5$  treated subjects.

- Overall summary of non-endocrine IMAEs leading to discontinuation by worst CTC grade (any grade, grade 3-4, grade 5) where immune modulating medication was initiated presented by Category / PT. This output will also be presented for CPS  $\geq$  5 treated subjects.
- Overall summary of endocrine IMAEs leading to discontinuation by worst CTC grade (any grade, grade 3-4, grade 5) presented by Category / PT. This output will also be presented for CPS  $\geq$  5 treated subjects.
- Overall summary of non-endocrine IMAEs leading to dose delay or reduction by worst CTC grade (any grade, grade 3-4, grade 5) where immune modulating medication was initiated presented by Category / PT. This output will also be presented for CPS  $\geq$  5 treated subjects.
- Overall summary of endocrine IMAEs leading to dose delay or reduction by worst CTC grade (any grade, grade 3-4, grade 5) presented by Category / PT. This output will also be presented for CPS  $\geq$  5 treated subjects.
- Summaries of time-to onset and time-to resolution of non-endocrine IMAEs where immune modulating medication was initiated presented by Category. This output will also be presented for CPS  $\geq$  5 treated subjects.
- Summaries of time-to onset and time-to resolution of endocrine IMAEs presented by Category. This output will also be presented for CPS  $\geq$  5 treated subjects.

A by-subject listing of IMAEs will be provided. By-subject listings of time-to resolution for longest IMAEs cluster (any grade and grade 3-5 in separate summaries) will also be provided. For new studies which collect investigator assessment of potential IMAE data, a by-subject listing of AEs considered as immune-mediated events per investigator but not qualified for IMAEs definition will also be provided.

In addition, for all nivolumab treated subjects who experienced at least one IMAE, the following data presentation will be provided:

- Summary of subjects who were re-challenged with nivolumab by IMAE category, with extended follow-up. This output will also be presented for CPS  $\geq$  5 treated subjects.

For these, re-challenge is considered to have occurred when last nivolumab infusion was administered after the onset of an IMAE.

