4.5.1.2 Dose Delay Criteria for Nivolumab and/or Ipilimumab Therapy

Nivolumab and/or ipilimumab administration should be delayed for the following:

- Any Grade ≥ 2 non-skin, drug-related AE, with the following exception:
 - Grade 2 drug-related fatigue does not require a treatment delay.
- Grade 2 drug-related creatinine, AST, ALT and/or Total Bilirubin abnormalities
- Any Grade 3 skin, drug-related AE
- Any Grade 3 drug-related laboratory abnormality (excluding AST, ALT or Total Bilirubin), with the following exceptions for lymphopenia, and asymptomatic amylase or lipase abnormalities:
 - Grade 3 lymphopenia does not require dose delay
 - Any Grade ≥ 3 drug-related amylase or lipase abnormality that is not associated with symptoms or clinical manifestations of pancreatitis does not require dose delay.
- Any AE, laboratory abnormality, or intercurrent illness which, in the judgment of the investigator, warrants delaying the dose of study medication.

Subjects receiving ipilimumab in combination with nivolumab who have drug-related toxicities that meet the criteria for dose delay should have both drugs (ipilimumab and nivolumab) delayed until retreatment criteria are met (exceptions apply to the retreatment criteria after dose delay of ipilimumab and nivolumab for Grade ≥ 3 amylase and lipase abnormalities that are not associated

with symptoms or clinical manifestations of pancreatitis and that are attributed to ipilimumab and/or nivolumab).

Subjects who require delay of nivolumab and ipilimumab should be re-evaluated weekly or more frequently if clinically indicated and resume nivolumab and/or ipilimumab dosing when re-treatment criteria are met.

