#### 7.1.1 ***Adverse Events, Serious Adverse Events, Multiple Events, Select Adverse Events, Other Events of Special Interest and Immune-Mediated Adverse Events***

Drug-related AEs are those events with relationship to study drug “Related”, as recorded on the CRF. If the relationship to study drug is missing, the AE will be considered as drug-related.

Serious adverse events consist of AEs deemed serious by the Investigator and flagged accordingly in the CRF and clinical database.

Adverse events leading to study drug discontinuation are AEs with action taken regarding study drug(s) = “Drug was discontinued”.

Adverse events leading to dose delay are AEs with action taken regarding study drug(s) = “Drug was delayed”.

Adverse events leading to dose reduction are AEs with action taken regarding study drug(s) = “Dose was reduced”.

Adverse events will be coded using the Medical Dictionary for Regulatory Activities (MedDRA), and the most recent version of the dictionary at the time of the database lock will be used. Adverse events results will be graded for severity using NCI Common Terminology Criteria for Adverse Events (CTCAE) and the most recent version of the criteria at the time of the database lock will be used.

In the AE summary tables, unless otherwise specified, subjects will be counted only once at the Preferred Term (PT), only once at the System Organ Class (SOC), and only once at subject level for the counting of total number of subjects with an AE. The AE tables will be sorted by the SOCs and then PTs. SOC will be ordered by descending frequency overall and then alphabetically. PTs will be ordered within SOC by descending frequency overall and then alphabetically. The sorting will be done based on the ‘Any Grade’ column of the experimental arm when arms are presented side-by-side.

Unless otherwise specified, the AE summary tables will be restricted to on-treatment events regardless of the causality.

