### **7.1.1.3 Immune-Mediated Adverse Events (US Submission)**

In order to further characterize AEs of special clinical interest, analysis of immune-mediated AEs (IMAE) will be conducted. IMAEs are specific events (or groups of PTs describing specific events) that include pneumonitis, diarrhea/colitis, hepatitis, nephritis/renal dysfunction, rash, endocrine (adrenal insufficiency, hypothyroidism/thyroiditis, hyperthyroidism, diabetes mellitus, and hypophysitis), and other specific events, considered as potential immune-mediated events by investigator that meet the definition summarized below:

- those occurring within 100 days of the last dose,
- regardless of causality,
- treated with immune-modulating medication (of note, endocrine AEs such as adrenal insufficiency, hypothyroidism/thyroiditis, hyperthyroidism, diabetes mellitus, and hypophysitis are considered IMAEs regardless of immune-modulating medication use, since endocrine drug reactions are often managed without immune-modulating medication).
- with no clear alternate etiology based on investigator assessment, or with an immune-mediated component

The list of MedDRA preferred terms used to identify IMAEs is revisited quarterly and updated accordingly. The preferred terms used for the selection at the time of the database lock by categories will be provided.

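### SAP 7.6.7 counts any nivolumab infusion after IMAE onset as re-challenge, so subjects who never stopped dosing are pooled with those who resumed after a hold

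*SAP*

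**What the plan says.** SAP Section 7.6.7 adds one presentation "for all nivolumab treated subjects who experienced at least one IMAE": a "Summary of subjects who were re-challenged with nivolumab by IMAE category, with extended follow-up". It then defines the term: "re-challenge is considered to have occurred when last nivolumab infusion was administered after the onset of an IMAE". Nothing else in the SAP or protocol adds a condition that nivolumab was held, that the event resolved, or that a minimum gap passed.

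SAP Section 7.1.1.3 sets what counts as an IMAE. Events qualify "regardless of causality". They must have been treated with immune-modulating medication, except that endocrine events "are considered IMAEs regardless of immune-modulating medication use". There must also be no clear alternate cause, or an immune-mediated component. The tables in 7.6.7 cover events of any grade.

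Protocol Section 4.5.1.2 sets when nivolumab must be delayed. The main triggers are a Grade 2 or higher "non-skin, drug-related AE, with the following exception" (Grade 2 fatigue), and "Any Grade 3 skin, drug-related AE". A further clause lets the investigator delay for any event that he or she judges to warrant it. Protocol Section 4.5.1.4 ties resumption to resolution of the drug-related event to Grade 1 or baseline, with listed exceptions.

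The SAP already uses two sources that identify a hold: the action-taken field on the adverse event record (Section 7.1.1) and a dosing-date rule for an actual delay (Section 7.4.2.1, Table 7.4.2.1-1). The re-challenge rule refers to neither.

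**The concern.** In ordinary use, re-challenge means that a drug was stopped for an event and then given again. The protocol's own provisions on delaying and resuming follow that sequence. The SAP applies the word to a wider set: everyone who received at least one infusion after onset. That includes a subject who took the next routine dose during a mild event. It also includes a subject dosed once after a mild onset whose nivolumab was then stopped for good when the event worsened.

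This is the only output in Section 7.6.7 about nivolumab given again after an IMAE. A reader of the study report would naturally take its count as the number of subjects who resumed after an immune-mediated event. If an unknown share never interrupted treatment, that reading is wrong, and the table gives no means of correcting it.

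**Working it through.** No sample size, power or event count lies behind this rule, so the check is logical.

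**Step 1: what the rule tests.** The last infusion falls after onset exactly when at least one infusion falls after onset. A hold is not an input, so uninterrupted dosing satisfies the rule.

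**Step 2: whether an IMAE can occur without a mandatory hold.** The table sets the IMAE definition (SAP 7.1.1.3) beside the delay criteria (Protocol 4.5.1.2).

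| Event | Counts as IMAE? | Delay required? | Labelled re-challenged if dosed after onset? |
|---|---|---|---|
| Grade 1 endocrine, drug-related, no immune-modulating medication | Yes | No: below Grade 2 | Yes, without any hold |
| Grade 1–2 skin, drug-related, given immune-modulating medication | Yes | No: below Grade 3 | Yes, without any hold |
| Recorded as unrelated, other IMAE conditions met | Yes | No: the specific criteria concern drug-related events | Yes, without any hold |
| Grade 2 non-skin (not fatigue), drug-related, other IMAE conditions met | Yes | Yes | Yes, after a hold |
| Grade 1 non-endocrine, no immune-modulating medication | No | Not relevant | Not counted |

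The first three rows can enter the count with no interruption. The fourth is a resumption after a hold. All four receive the same label. The last row marks a limit: untreated mild non-endocrine events are not IMAEs and do not contribute.

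**Step 3: whether another output separates them.** Section 7.6.7 tabulates IMAEs leading to dose delay or reduction, and IMAEs leading to discontinuation. These tables are not linked to a later infusion, and the first combines delay with reduction. They do not give the number delayed for an IMAE and then dosed again.

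**Step 4: size.** The documents contain no number of IMAEs, of holds, or of subjects dosed after onset. The proportion of the count that was never interrupted cannot be derived.

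**The case against.** The strongest reply is that the term is explicitly defined, the output is a descriptive count, and the information exists elsewhere. Section 7.6.7 provides the delay and discontinuation tables and a by-subject IMAE listing, Section 7.4.1 provides a dosing listing, and the table layouts sit in a Data Presentation Plan that is not among these documents. This stands in part. The split could be rebuilt from subject-level listings, but the planned summary as described does not show it.

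A second reply is that the unheld group is narrow. Non-endocrine IMAEs must have been treated with immune-modulating medication. Investigators may hold for any event they judge to warrant it. Protocol 4.5.1.4 also requires subjects given systemic corticosteroids for drug-related toxicity to be off them, or at no more than 10 mg/day prednisone equivalent, before resuming. Many drug-related IMAEs of Grade 2 or higher will therefore have had a real hold. This limits where the mixing occurs but does not remove it.

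A third reply is directed at the obvious remedy of redefining re-challenge to require a delay, and it is sound. Under Protocol 4.5.1.4 an event that resolves before the next scheduled dose leads to dosing on time, so no delay would be recorded and the subject would drop out. Under Protocol 4.5.2.2 all drugs should be delayed if either the nivolumab or the chemotherapy criteria are met, so a chemotherapy-driven delay could be counted against an unrelated IMAE. The footnotes to Table 7.4.2.1-1 place FOLFOX-treated subjects under every-3-week nivolumab and XELOX-treated subjects under every-2-week nivolumab, whereas SAP Section 2.1 has the opposite pairing. Those passages must be reconciled before the delay windows are used.

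**Conclusion.** The point holds as a labelling and presentation defect. The count pools continued dosing with resumption after a hold, and so cannot be read as experience with resuming nivolumab. It is minor: descriptive safety only, with no bearing on an efficacy test or alpha. The mixing falls mainly among low-grade endocrine events, low-grade skin events given immune-modulating medication, and events judged unrelated. Its extent is unknown.

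Two stronger readings are tempting, and the documents do not support them.

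- A reader might infer that a high re-challenge rate is expected even if nobody resumed after a hold. With constant onset risk over treatment length T plus the 100-day window, the chance that onset precedes the last infusion is T/(T+100): 60/160 = 38%, 100/200 = 50%, 180/280 = 64%, 365/465 = 78%. This assumes that an IMAE never alters dosing, which conflicts with the delay and permanent-discontinuation rules in Protocol 4.5.1.2 and 4.5.1.5. It also assumes constant risk and full 100-day observation. It does not predict this trial's rate.
- A reader might infer that the pooling dilutes a recurrence result. Section 7.6.7 names no recurrence outcome. It mentions extended follow-up without saying what will be reported.

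**What to change.** Keep the existing count but label it as nivolumab given after IMAE onset. Within each IMAE category, split it into:

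- (a) subjects whose nivolumab was delayed for that IMAE, according to the action-taken field with nivolumab as the delayed drug, and was then given again; and
- (b) subjects dosed after onset with no recorded nivolumab delay for that IMAE.

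State in the SAP where to show a subject who was dosed after onset, then delayed for the event and not dosed again, since neither row covers that case. Add a footnote that row (b) includes events that resolved before the next scheduled dose.

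Section 7.1.1 describes action taken for study drugs in general, so confirm that the record can be tied to nivolumab. If a derived delay is used as support, apply the window for the subject's actual nivolumab schedule, after the Table 7.4.2.1-1 footnotes have been reconciled with the dosing section.

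No new data are needed, because the SAP already relies on action taken and dosing dates. The cost is SAP wording, some programming, and a layout that differs from the nivolumab-plus-chemotherapy report, which SAP Section 11 says was written before version 5.0. Under SAP Section 10 the nivolumab-plus-ipilimumab report comes at the second analysis time point, so the change can be made there. Because the overall count is kept, the two reports remain comparable on that figure.

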### **7.6.8 Other Events of Special Interest**

OEOSI will be summarized by treatment group for each category.

The following analyses will be conducted using the 100-day safety window:

- Overall summary of OEOSI by worst CTC grade (any grade, grade 3-4, grade 5) presented by Category / PT
- Overall summary of drug-related OEOSI by worst CTC grade (any grade, grade 3-4, grade 5) presented by Category / PT

A by-subject listing of OEOSI will be provided.

### **7.6.9 Multiple Events**

The following summary tables will be provided:

- A table showing the total number and rate (exposure adjusted) of occurrences for all AEs.
- A table showing the total number and rate (exposure adjusted) of occurrences for AEs occurring in at least 5% of subjects in any treatment group.

A listing displaying the unique instances of all AEs, ie, after duplicates have been eliminated and overlapping and contiguous occurrences of the same event (ie, same PT) have been collapsed will be provided. No formal comparisons will be made between treatment groups.

### **7.6.10 Laboratory Parameters**

The analysis population for each laboratory test is restricted to treated subjects who underwent that laboratory test.

A by-subject listing of differences in categorization of SI and US laboratory test results will be provided.

#### **7.6.10.1 Hematology**

The following will be summarized by treatment group as shift table of worst on-treatment CTC grade compared to baseline CTC grade per subject: hemoglobin (HB), platelets, white blood counts (WBC), absolute neutrophils count (ANC) and lymphocyte count (LYMPH). This output will also be presented for CPS  $\geq 5$  treated subjects.

The analyses will be conducted using the 30-day safety window.

A by-subject listing of these laboratory parameters will be provided.

#### **7.6.10.2 Serum Chemistry**

The following will be summarized by treatment group as shift table of worst on-treatment CTC grade compared to baseline CTC grade per subject: ALT, AST, total bilirubin and creatinine. This output will also be presented for CPS  $\geq 5$  treated subjects.

The analyses will be conducted using the 30-day safety window.

A by-subject listing of these laboratory parameters will be provided.

#### **7.6.10.3 Electrolytes**

The following will be summarized by treatment group as shift table of worst on-treatment CTC grade compared to baseline CTC grade per subject: sodium (high and low), potassium (high and low), calcium (high and low) and Glucose Serum (fasting hyperglycemia and hypoglycemia regardless of fasting status). This output will also be presented for all  $\geq 5$  treated subjects.

The analyses will be conducted using the 30-day safety window.

A by-subject listing of these laboratory parameters will be provided.

